## 4.4.2.3 Prophylactic and On-demand FIX Replacement Therapy

As mentioned in section 4.3.4.3 administration on demand FIX replacement therapy in the 1 year period prior to screening has been registered. All these data will be listed. The on-demand FIX replacement therapy products used and the total dose used will be summarised for each cohort for this 1 year period prior to screening.

From Visit 1 and throughout the entire trial participation period, patients have been asked to document use of FIX replacement therapy in an e-diary. Two different modules in the e-diary will be used for registering prophylactic and on-demand FIX replacement therapy respectively.

The patient e-diary modules will include questions with respect to

- Date/time of administration
- Drug name
- Dose

All data will be presented in listings. The listings will be split two parts: a) the period from screening and until the end of tapering b) the period from end of tapering until end of trial/cut-off date in an interim analysis.

The use of prophylaxis and on-demand treatment in general will be summarized according to product and type (on-demand or prophylaxis). The summarises will be performed by cohort and overall. Furthermore, the total on-demand use for each patient (regardless of product) for the post tapering period will be summarized by cohort. The total dose for each patient will be annualized i.e. the dose will be adjusted for the length of the observation time (end of tapering until end of trial/cut-off date in an interim analysis) for the patient in question.

A listing will be generated combining on a patient level the information for the 1-year period prior to screening and for the post tapering-period including on-demand FIX-replacement therapy (annualized), bleeding episodes and annualized bleeding rates.

# 4.4.2.4 PRO – CCI

**CCI** scores will be computed using the **CCI** user manual. For each of the 8 domains as well as for the physical and mental health total scores descriptive statistics for absolute values and change from baseline will be provided by visits, cohorts and overall. For each domain the progression over time will also be presented, using change from baseline scores.

In case the **CCI** scores were not determined at the scheduled visit, it will be checked if **CCI** scores were determined at an adjacent (unscheduled) date , and if so those data will be used as a substitute. These decisions will be documented by Larix and agreed to by the responsible person at uniQure.

# 4.5 Safety

Safety parameters will be evaluated for the full analysis set.

*Larix A/S - Strictly Confidential* F501-0-1–5 SAP Template Page 19 of 34

Date: 27MAY2021

CT-AMT-060-01 EudraCT No.: 2013-005579-42 Statistical Analysis Plan Final no. 05 Page 20 of 34

# 4.5.1 Adverse Events – Primary Safety Endpoint

All reported adverse events will be coded using the Medical Dictionary for Regulatory Activities (MedDRA version 17.1).

An AE is considered related with the use of drug if the relationship to IMP is classified as either 'Probably related' or 'Possibly related'. A related AE is referred to as an Adverse Drug Reaction (ADR).

An adverse event is defined as treatment emergent (TEAE) when onset of the event is after the administration of the IMP. In case an AE starts the same day of IMP administration and the exact time is missing, it will be defined as Treatment Emergent AE.

Adverse events for special notification are determined through the eCRF.

In case of missing or incomplete onset dates of AEs the onset date will be imputed such that the event starts as early as possible based on the partial date. Furthermore, if the AE could be treatment emergent based on the missing or incomplete date, then the AE will be regarded as treatment emergent.

Furthermore, missing values for AEs will be treated as missing except for causality and intensity. If causality is missing for a TEAE, the TEAE will be regarded as 'Probably related'. If causality is missing for an AE with onset before administration of trial drug, the AE will be regarded as 'Unlikely related'. If the intensity is missing the intensity of the AE will be regarded as severe. In case seriousness is missing this should be queried again since seriousness cannot be imputed as 'Yes' by default, since this would affect the reconciliation between trial data base and registry of SAEs.

All TEAEs will be tabulated, while pre-treatment AEs will only be listed.

An AE overview summary table will be prepared including the number of patients reporting at least one AE, the percentage of patients (%) with at least one AE, and the number of events (E) reported, for the following categories:

- TEAEs
- Related TEAEs
- Deaths
- Serious TEAEs
- Severe/Moderate/Mild TEAEs
- TEAEs leading to discontinuation of study treatment (defined as action taken='Drug withdrawn' on the AE form)
- TEAEs qualifying for special notification

Treatment-emergent adverse events will be summarized by Dictionary level, i.e., SOC and PT for MedDRA. The table will display the total number of patients reporting at least one AE, the percentage of patients (%) with at least one AE, and the number of events (E) reported. AEs will be presented by SOC and Preferred Term sorted in decreasing frequency of occurrence.

Summary tables will be prepared for:

- All TEAEs
- All Related TEAEs
- Deaths
- Serious TEAEs
- Severe/moderate/mild TEAEs
- Any TEAEs leading to discontinuation of study treatment

Larix A/S - Strictly Confidential F501-0-1–5 SAP Template Page 20 of 34

Date: 27MAY2021

Final no. 05

Page 21 of 34

CT-AMT-060-01 EudraCT No.: 2013-005579-42 Statistical Analysis Plan

TEAEs qualifying for special notification

Data listings will be provided for:

- All pretreatment AEs sorted by patient no.
- All TEAEs sorted by patient no.
- All related AEs sorted by patient no.
- Serious AEs sorted by patient no
- AEs leading to discontinuation study treatment
- Deaths sorted by patient no
- TEAEs qualifying for special notification sorted by patient no

## 4.5.2 Secondary Safety Endpoints

All data described in this section will simply be presented in listings. The listings will include calculated change from baseline (Visit 2, day 1) where applicable.

#### 4.5.2.1 Vector DNA in Semen, Blood, Saliva, Nasal Secretions, Urine and Faeces

Sampling of the following types of matrix will be performed to determine Vector DNA levels: Blood, saliva, nasal secretions, urine, faeces and semen. Sampling time points are given as: Visits 2-35.

Sampling should continue for the individual patient and for a specific matrix until 3 consecutive negative samples have been detected for the patient for that particular type of matrix.

All data will be listed. Furthermore, each individual patient profile will be presented graphically per matrix.

Time to first shedding negative will be defined for each type of matrix and each patient as the post treatment time point where a negative result is measured for the first time in a consecutive order of 3 or more time points with a negative result. Negative result is defined as a result of either '0' or 'LOD'. The time to first shedding negative will be flagged on the above-mentioned listings and will also be summarized.

#### 4.5.2.2 Neutralizing Antibodies to AAV5

Blood sampling for measurement of neutralizing antibodies to AAV5 will take place at the time points indicated in the flowchart in the protocol, section 5.

All data will be listed.

#### 4.5.2.3 Total (IgM and IgG) Antibodies to AAV5

Blood sampling for measurement of total (IgG and IgM) antibodies to AAV5 will take place at the time points indicated in the flowchart in the protocol, section 5.

All data will be listed.

Larix A/S - Strictly Confidential F501-0-1–5 SAP Template Page 21 of 34

Date: 27MAY2021

CT-AMT-060-01 EudraCT No.: 2013-005579-42 Statistical Analysis Plan Final no. 05 Page 22 of 34

# 4.5.2.4 AAV5 Capsid-specific T cells

Sampling for AAV5 capsid-specific T cells will take place at the time points indicated in the flowchart in the protocol, section 5.

It is noted that the data provided by the laboratory are given in a unit of SFC per 300000 PBMCs. All measurement will therefore be multiplied by a factor 10/3 in order to present the data in unit SFC per 1 million PBMCs.

All data will be listed and data will also be presented in plots of patient individual profiles.

#### 4.5.2.5 Antibodies to FIX

Blood sampling for measurement of anti-FIX antibodies will take place at the time points indicated in the flowchart in the protocol, section 5.

All data will be listed.

#### 4.5.2.6 FIX Inhibitors

Blood sampling for measurement of FIX inhibitors will take place at the time points indicated in the flowchart in the protocol, section 5.

The investigator may instigate that blood samples for FIX inhibitors are taken at additional visits in case (of suspicion) of detection of inhibitors (Nijmegen modified Bethesda assay – Bethesda unit >= 0.6).

A patient is said to suffer from inhibitors (Bethesda Unit  $\geq 0.6$ ) if tested positive for inhibitors at two consecutive test performed preferably within two weeks. If a patient has confirmed inhibitor and continues with no change to treatment type for six weeks and the FIX inhibitor test is negative after that time, the inhibitor is classified as transient.

All data will be listed.

#### 4.5.2.7 Inflammatory Markers IL-1β, IL-2, IL-6, INFγ, MCP-1

Blood sampling for measurement of IL-1 $\beta$ , IL-2, IL-6, INF $\gamma$  and MCP-1 will take place prior to IMP administration and in the period up to 18 weeks after IMP administration:

- at Visit 2 (prior to IMP administration)
- at Visits 3 14 (weekly in weeks 1 12)
- at Visits 15 17 (bi-weekly in weeks 14, 16, 18).

All data will be listed.

## 4.5.3 Other Safety Endpoints

Larix A/S - Strictly Confidential F501-0-1–5 SAP Template Page 22 of 34

Date: 27MAY2021

CT-AMT-060-01 EudraCT No.: 2013-005579-42 Statistical Analysis Plan Final no. 05 Page 23 of 34

# 4.5.3.1 Physical Examination

A physical examination will be performed at all visits. At Visit 2 (dosing visit with overnight stay) the physical examination will be performed both prior to IMP administration and at the end of the overnight stay (i.e., at 24 hours after IMP administration).

The physical examination will include general appearance and bedside examination of the following body systems: Lymph nodes, mouth and throat, eyes, ears, lungs, abdomen, extremities, musculoskeletal system, neurological system and skin.

The evaluation of each body system will be recorded in the eCRF as "normal" or "abnormal". Abnormalities will also be recorded in the eCRF.

All data will be presented in listings.

## 4.5.3.2 Vital Signs and Body Temperature

Blood pressure, pulse, and body temperature will be measured at all visits. At Visit 2 (dosing visit with overnight stay) blood pressure and pulse will be measured prior to IMP administration and at the following approximate time points after IMP administration: 0.5, 1, 2, 3, 4, 6, 8, 12 and at 24 hours.

All data including change from baseline (Visit 2, day 1) will be listed and data will also be presented in plots of individual profiles.

#### 4.5.3.3 Serum Chemistry

At the time points indicated in the flowchart in the protocol, section 5 the following parameters are measured:

Serum electrolytes (sodium, potassium), creatinine, gamma-glutamyltransferase ( $\gamma$ GT), aspartate aminotransferase (AST), alanine transaminase (ALT), alkaline phosphatase (ALP), C-reactive protein (CRP), albumin, total bilirubin and glucose (non-fasting)

All data will be listed. The data will from the parameters amma-glutamyltransferase ( $\chi$ GT), aspartate aminotransferase (AST), alanine transaminase (ALT), CRP, albumin, and total bilirubin will also be presented in plots of individual profiles. On the listing reference range and flag indicating if measurement in question is outside the reference range will appear. The reference range for the parameter in question will also appear on profile plots.

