13.6 Adverse Events Qualifying for Special Notification

New AEs potentially related to the conduct of the trial or the development of the Advanced Therapy Medicinal Products (ATMP) and likely to affect the safety of the subjects should be

Clinical Trial Protocol

Trial ID: CT-AMT-060-01

uniQure

reported and followed in the same manner as SAEs (see [Section 13.3](#) and [Section 13.7](#)). Note that the AEs may be serious or non-serious by definition (see [Section 13.1](#)).

In addition, the following (S)AEs qualify for special notification as they are seen as safety issues of particular concern for ATMPs ([ENTR/F/2/SF/dn D\(2009\) 35810. Brussels, 03/12/2009](#)) and gene therapy medicinal products ([EMEA/CHMP/GTWP/60436/2007](#)):

- AEs related to the IMP administration procedure (intravenous infusion)
- Suspected or confirmed cases of opportunistic or serious infections that in the Investigator's opinion might be related to the IMP
- Unexpected reactions (e.g. hypersensitivity, immunological, toxic or other as consequence of a change in the construction or function of the viral vector [e.g. generation of replication competent virus])
- AEs related to product failure (including lack of efficacy)
- Confirmed FIX inhibitors
- Thromboembolic events
- Transaminase elevation > 1.5 times baseline value
- Allergic reactions
- AEs that could be related to potential off-target expression
- Development of any new/recurrent cancer.

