19.2.1 Trial Stopping Rules

As the trial is a one-dose trial, stopping rules are relevant only for the recruitment period. Independently of any changes to the recruitment, subjects who have already been dosed will be followed as per protocol to the end of trial.

Clinical Trial Protocol

Trial ID: CT-AMT-060-01

uniQure

The data monitoring committee will prior to dosing review data as detailed below and recommend whether:

- The next subject could be dosed
- Further data would be required before the next dosing
- No further dosing should take place i.e. subject recruitment is discontinued.

The following events may lead to a decision to pause dosing, i.e. stop subject recruitment to allow for evaluation and assessment of the implications of the event for further subject dosing:

1. A more than 5-fold increase in ALT, AST or both in one or more subjects after IMP administration which is not manageable by steroid rescue treatment implemented according to American Association for the Study of Liver Diseases (AASLD) guidelines. (Manns et al. 2010)
2. An SAE judged as probably or possibly related to the IMP and which pose either an immediate risks to subject's health or is likely to adversely affect the subject's health long term. This includes events classified as AEs qualifying for special notification (Brussels, 03/12/2009, ENTR/F/2/SF/dn D(2009) 35810; EMEA/CHMP/GTWP/60436/2007) as listed in Section 13.6, if these are judged as probably or possibly related to the IMP. The development of an inhibitor towards FIX in one subject is not a cause for stop of subject recruitment, however the development of an FIX inhibitor in more than one subject should lead to pausing of dosing and further investigations of causal relationship
3. Death of a subject, after having received the IMP, that is judged as related to the IMP
4. The occurrence of a malignancy at any point after gene transfer that is judged as probably or possibly related to the IMP.

Decision to start Cohort 2

If none of the events listed above have occurred the data monitoring committee may recommend that Cohort 2 can be initiated. If one or more of these events have occurred, dosing will be paused while the event(s) is/are further investigated including the implications for further dosing and dose level.

Decision to dose the next subject within a cohort

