# Statistical analyses and presentation of data

# 4.1 General Considerations

All reporting will be made for the Full Analysis Set. Reporting may also be made for other analysis populations (PP Analysis Set), or subgroups of patients based on for example genotype.

Data will be presented in tables and listings following the principles in ICH E3 guideline regarding (structure and content of clinical reports). On the listings, cohort will appear in a separate column and the listings will be sorted by cohort/dose and patient ID within cohort/dose. In the tables data from each cohort/dose will be presented in separate columns. For selected endpoints data will also be presented graphically.

All data will be listed, including unused and spurious data. Imputation of missing or partial data will not be done unless explicitly described. In the case of imputation of missing data, both the original missing or partial data and the imputed values will be listed. Continuous data will be shown in listings with the same precision as captured.

Summary tables will show the number of non-missing values

Numerical data will be presented in summary tables by number of patients, arithmetic mean, median, standard deviation, minimum and maximum and CV (%). Categorical data will be presented by number and percent of patients as well as the number of events (where applicable).

Patient level summaries (listings) will be presented adjusted for observation time where applicable. This includes but is not limited to the annualized rate of selected signs and symptoms and annualized bleeding rate.

In general, laboratory parameters will be presented by visit and will include categorization of parameters into low/normal/high where applicable. For some of the laboratory parameters a measurement of '< x' (x being a numerical value) are occasionally registered. In such a case a value equal to  $0.5^*x$  is used when summary tables are generated, whereas the '< x' will be reported in listings. This recalculation for use in summary tables will also be documented in the ADRG.

The distance in days between a measurement/event and the trial drug administration date is calculated as follows:

- If date(measurement/event) < date(trial drug administration): Distance in days = date(measurement/event) – date(trial drug administration)
- If date(measurement/event) >= date(trial drug administration): Distance in days = date(measurement/event) – date(trial drug administration) + 1

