# 4.6.5 AST and ALT for Local Monitoring of Patients

At the time points indicated in the protocol, section 12.3.1, Table 4 blood samples have been taken and aspartate aminotransferase (AST), alanine transaminase (ALT) is measured the local laboratory. The results are entered in the eCRF.

These data will be presented in a listing.

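### The SAP text specifies no ratio to baseline for ALT or AST, so the protocol's 1.5-fold and 1.5–2-fold baseline criteria have no laboratory derivation behind the investigator-reported events

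*SAP*

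**What the plan says.** **SAP, central laboratory.** Section 4.5.3.3 lists all chemistry and adds: "On the listing reference range and flag indicating if measurement in question is outside the reference range will appear". ALT and AST are among the parameters plotted by subject, and "The reference range for the parameter in question will also appear on profile plots". This follows the general rule in 4.1 that laboratory presentation "will include categorization of parameters into low/normal/high where applicable". No change from baseline or ratio is mentioned for chemistry.

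**SAP, local laboratory.** Section 4.6.5 says of local AST and ALT: "These data will be presented in a listing". No flag or plot is mentioned. Local FIX activity (4.6.3), by contrast, is given a reference range and a flag.

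**SAP, where baseline is used.** For the secondary safety endpoints, 4.5.2 says "The listings will include calculated change from baseline (Visit 2, day 1) where applicable". For vital signs, 4.5.3.2 says "All data including change from baseline (Visit 2, day 1) will be listed". Serum chemistry sits in 4.5.3.3 and is covered by neither sentence.

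**Protocol.** Section 13.6 makes this an event for special notification: "Transaminase elevation > 1.5 times baseline value". Section 11.2.3 ties its corticosteroid recommendation to an ALT increase above 1.5–2-fold of the Day 1 pre-dose level. Section 19.2.1 lists among the events that may pause dosing "A more than 5-fold increase in ALT, AST or both in one or more subjects after IMP administration", if not manageable with steroids; it does not say what the rise is measured against.

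**Reporting of the events.** SAP 4.5.1 takes special-notification events from the eCRF and gives them a summary table (shell 14.3.1.10, which has transaminase and ALT rows) and a listing.

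**The concern.** The laboratory flag and the protocol criteria measure different things. The flag asks whether a value lies outside a population range. The criteria in protocol 11.2.3 and 13.6 ask whether it has risen relative to the subject's own pre-dose value. A subject with a low-normal baseline can meet the second without touching the first.

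Immune-mediated liver toxicity is a named risk in protocol 6.7, and that section relies on twice-weekly monitoring to week 12 to detect it. Safety is the primary objective. The number of subjects meeting the 1.5-fold criterion will be read from adverse events that investigators recognised and entered. If a rise within the normal range was not entered, no planned derivation would reveal the omission. If the peak fell at one of the second weekly visits, it would appear only in a plain listing of local values.

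**Working it through.** The plan states no figure on this point, so there is nothing to reproduce. The check is threshold algebra plus a count of sampling times.

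**1. When a fold-rise stays inside the range.** With baseline b, upper limit U and post-dose value k × b, the value exceeds the upper limit only if k × b > U. It carries no flag when b ≤ U/k. The documents give no upper limit, so U = 30, 40 and 50 U/L are assumptions.

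| Post-dose value, k × baseline | U/k as share of U | U = 30 | U = 40 | U = 50 |
|---|---|---|---|---|
| 1.5 | 66.7% | 20.0 | 26.7 | 33.3 |
| 2 | 50.0% | 15.0 | 20.0 | 25.0 |
| 5 | 20.0% | 6.0 | 8.0 | 10.0 |

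A rise just over k-fold from a baseline below the entry shown has no reference-range flag.

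**2. Examples at U = 40.**
- Baseline 18: 18 × 1.51 = 27.2 and 18 × 2.01 = 36.2. Neither is flagged.
- Baseline 26: 26 × 1.51 = 39.3, not flagged; 26 × 2.01 = 52.3, flagged.
- Baseline 12: 12 × 5.01 = 60.1, flagged.

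**3. The opposite error.** Protocol 9.3 excludes screening ALT or AST only above 2 × U. A subject enrolled between 1 × U and 2 × U who stays stable would be flagged at every visit with no rise at all.

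**4. Sensitivity to the wording of protocol 11.2.3.** If the increase itself must exceed 1.5–2 times baseline, the value is above 2.5–3 times baseline. The cut-offs become 1/2.5 = 40% and 1/3 = 33% of U. The gap narrows but remains.

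**5. Scheduled post-dose ALT/AST samples to week 26** (protocol Tables 12-2 and 12-4).
- Local: 1 (24 hours) + 12 (weekly) + 12 (second weekly visit) + 6 (weeks 14 to 24) + 1 (week 26) = 32.
- Central: 12 (weeks 1–12) + 4 (weeks 16, 20, 24, 26) = 16.
- Local with no central counterpart: 1 (24 hours) + 12 (second weekly visit) + 3 (weeks 14, 18, 22) = 16, and 16/32 = 50%.

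**6. Feasibility.** Tables 12-2 and 12-4 both schedule a pre-dose sample at Visit 2, so each laboratory has its own baseline.

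**The case against.** The strongest case against is that the 1.5-fold rise is itself a reportable event. Protocol 13.4 requires it within 24 hours, and the SAP gives such events a table and a listing. A reader might infer that these rises go unreported; the documents do not support that. What stands is narrower: this route depends on investigator entry, and nothing in the SAP text checks it against the laboratory values.

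A reader might also infer that the number of subjects meeting the criterion cannot be found. With a minimum of 10 subjects and up to 2 more, and with all values listed including pre-dose ones, it can be counted by hand. Central ALT and AST are also plotted (Figures 14.3.5.17 to 14.3.5.20). The plan simply does not do the count.

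It is tempting to say that every liver criterion is affected. The >5-fold rule names no comparator. Against baseline, such a rise stays in range only if baseline is below a fifth of the upper limit; against the upper limit, it is always flagged. That rule also concerns the recruitment period and is reviewed by the data monitoring committee, not through these listings.

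Protocol Table 6-3, with prednisolone-treated ALT peaks of 36 and 43 IU/L, might be read as showing treated rises inside the normal range. It does not: it marks normal subjects as WNL and gives numbers for the others. It also concerns an AAV8 vector.

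Finally, SAP section 7 makes the shells part of the SAP, and the shells for Listings 16.2.8.13 and 16.2.8.18 were removed from the public file. A change-from-baseline column or a flag there cannot be excluded. The public list of table shells does, however, contain no ALT or AST laboratory table.

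The SAP does follow the protocol's general plan for low/normal/high categories (protocol 14.2), so this is a mismatch with the liver criteria and not a breach of the planned analysis.

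**Conclusion.** The point holds in a limited form. On the public text, the SAP flags central ALT and AST only against the reference range, lists local values without a flag or plot, and derives neither the >1.5 times baseline criterion nor the 1.5–2-fold criterion from laboratory data. The count of such rises rests on investigator-reported special-notification events with no laboratory check of completeness.

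The practical gap is at 1.5 to 2-fold. A rise just over 1.5-fold has no laboratory flag when baseline is below 67% of the upper limit; for just over 2-fold the figure is 50%. Half of the scheduled local time points to week 26 have no central counterpart. The U/L cut-offs rest on assumed upper limits of 30–50; the percentages do not.

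This does not show that any liver event would be missed, and it does not undermine the primary endpoint. It is a cheap improvement worth making because safety is the primary objective.

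**What to change.** In SAP 4.5.3.3 and 4.6.5:

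1. Derive ALT and AST as a ratio to the Visit 2 pre-dose value, with central and local results each against their own baseline, and show the ratio in the listings.
2. Flag listed values above the protocol's existing 1.5-fold and 2-fold baseline thresholds, keeping the reference-range flag.
3. Add local values to the individual ALT and AST plots.
4. Add one table by cohort of maximum post-dose ratio and week of peak.
5. Reconcile that table with the special-notification events in Table 14.3.1.10 and list any discrepancy.

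If the removed listing shells already contain a ratio or flag, say so in the SAP text and do only what is missing.

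Separately, two protocol wordings need to be reconciled by those responsible for the protocol: the comparator for the >5-fold rule in 19.2.1, and whether 11.2.3 refers to the post-dose value or to the size of the increase. The SAP should settle neither. Listing the ratio itself lets either reading of 11.2.3 be applied later.

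The cost is SAP wording, one derived variable per parameter and laboratory, one small table and a reconciliation step. No new data are needed and clinical management does not change.
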